## PROTOCOL AMENDMENT SUMMARY OF CHANGES TABLE

DOCUMENT HISTORY	
Document	Date
Amendment 2	This document
Amendment 1	25 August 2021
Original Protocol	17 May 2021

### Amendment 2 (26 November 2021)

**Overall Rationale for the Amendment:** In view of the slow rate of enrollment in the current study, the following changes were made to the inclusion and exclusion criteria to facilitate enrollment: the upper age limit for inclusion was adapted from less than 65 years to 75 years inclusive; a prior vaccination with a viral-vectored SARS-CoV-2 vaccine is allowed if administered at least 6 months prior to randomization; and it was clarified that co-participation in the observational phase of interventional studies can be allowed upon sponsor approval.

Emerging data from other ongoing clinical studies with the Ad26/protein preF RSV vaccine in participants in the age range of 60 to 75 years show that there is no substantial impact of age on vaccine-induced humoral immune responses, primary analysis pre-F ELISA antibody titers, and vaccine safety between older adults of 60 to 75 years of age. Based on these data, the sponsor considers an upper age limit of 75 years (inclusive) acceptable for this study.

Clinical studies with Janssen's Ad26-vectored SARS-CoV-2 vaccine have not shown a clear impact of baseline pre-existing Ad26 neutralizing antibodies on vaccine-induced responses. Based on these data, the sponsor considers a prior vaccination with a viral-vectored SARS-CoV-2 vaccine acceptable if administered at least 6 months prior to randomization. A minimal window of 6 months has been chosen since humoral immune response data evaluating a potential interference of the anti-vector responses with the vaccine-induced responses in consecutive dosing with viral-vectored vaccines with different inserts are not available to date. During further development of viral-vectored vaccines, data on potential interference will become available; at that point, the time window may be adjusted for future immunogenicity trials. The standard dosing window for viral-vectored SARS-CoV-2 vaccines in other Ad26.RSV.preF-based vaccine efficacy studies is 28 days and does not foresee an impact on safety.

Participants who participate in the observational phase of an interventional study at screening may also be eligible for the current study since participation in the observational phase without product administration will not adversely impact safety of the participants or have an impact on the vaccine-induced immune response.

Furthermore, additional language referring to laboratory diagnostic tests for the follow-up and assessment of potential adverse events of special interest (AESIs) was added. Clarifications were made with regards to some exclusion criteria, the recording of medical history, and the solicited and unsolicited AE assessments to be performed during phone call visits. It was clarified that screening and vaccination may be split into 2 visits in consultation with the sponsor or its delegate.

Additionally, a few minor updates were made in alignment with the latest Janssen protocol template.

The changes made to the clinical protocol VAC18193RSV3004 as part of Protocol Amendment 2 are listed below, including the rationale of each change and a list of all applicable sections. Changes made in previous protocol amendments are listed in Section 10.7 Appendix 7: Protocol Amendment History.

Section Number and Name	Description of Change	Brief Rationale
Title page 1.1 Synopsis 4.1 Overall Design 5.1 Inclusion Criteria	Inclusion Criterion 3 was amended to expand the eligible age range from 60 to less than 65 years, to 60 to 75 years inclusive.	To facilitate enrollment
5.2 Exclusion Criteria	Exclusion Criterion 10 was amended to allow the use of viral-vectored SARS-CoV-2 vaccines if administered at least 6 months prior to randomization.	To facilitate enrollment
5.2 Exclusion Criteria	Footnote for Exclusion Criterion 13 was updated to allow participants who participate in the observational phase of interventional studies to be enrolled in the study, if approved by the sponsor or its delegate.	To facilitate enrollment
5.2 Exclusion Criteria	A textual change was made to Exclusion Criterion 1 to clarify that participants with a history of malignancy within 5 years before screening, which is considered to have minimal risk of recurrence per investigator's judgement, can be enrolled.	Clarification
5.2 Exclusion Criteria	Exclusion Criterion 7 was amended to restrict the exclusion of participants on treatment with immunoglobulins to those immunoglobulins expected to impact the vaccine-induced immune response.	Clarification
1.2 Schema 1.3 Schedule of Activities 5 STUDY POPULATION 5.5 Criteria for Temporarily Delaying Study Vaccine Administration	It was clarified that screening and vaccination may be split into 2 visits in consultation with the sponsor or its delegate.	To allow more flexibility in timing of screening and vaccination in the best interest of participants.
1.3 Schedule of Activities	It was clarified that risk factors for blood clotting events and thrombocytopenia are to be collected and documented as part of the medical history at screening.	Clarification upon Health Authority request

Section Number and Name	Description of Change	Brief Rationale
1.3 Schedule of Activities	It was clarified that the severity of solicited and unsolicited AEs and the occurrence of special reporting situations are to be assessed also during the phone call visits at 7 and 28 days post-vaccination, following the recording period specified for these events.	Clarification
1.3 Schedule of Activities 8.3.6.1 Thrombosis with Thrombocytopenia Syndrome	Additional language referring to laboratory diagnostic tests for the assessment of potential AESIs was added.	To facilitate and simplify the local site management of follow-up testings in the event of potential AESIs.
4.4 End of Study Definition 8.3.1 Time Period and Frequency for Collecting AE, SAE, and AESI Information 8.3.3 Follow-up of AEs and SAEs and AESIs 10.2.4 Special Reporting Situations 10.2.6 PQC Handling 10.3.14 Study and Site Start and Closure 10.5 Appendix 5: Guidance on Study Conduct During a Natural Disaster	A few minor updates were made in alignment with the latest Janssen protocol template.	To align with the most recent Janssen protocol template.
Throughout the protocol	Minor grammatical, formatting, or spelling changes were made.	Minor errors were noted

## 1. PROTOCOL SUMMARY

### 1.1. Synopsis

#### A Randomized, Double-blind Phase 3 Study to Compare the Immunogenicity of Clinical Trial Material of an Ad26.RSV.preF-based Vaccine for Phase 3 with Clinical Trial Material Representative of Phase 2b in Adults Aged 60 to 75 Years

The respiratory syncytial virus (RSV) vaccine that will be investigated in the current study, the Ad26/protein preF RSV vaccine (VAC18193), is a combination of 2 vaccine components, administered as a single intramuscular (IM) injection:

- Ad26.RSV.preF (JNJ-64400141), a replication-incompetent adenovirus serotype 26 (Ad26) containing a DNA transgene that encodes the prefusion conformation-stabilized F protein (pre-F) derived from the RSV A2 strain.
- RSV preF protein (JNJ-64213175), a recombinant pre-F protein derived from the RSV A2 strain.

The aim of this study is to demonstrate the non-inferiority of the Phase 3 clinical trial material (CTM) compared with Phase 2b CTM\*, as used in the proof of concept study (VAC18193RSV2001) in which efficacy of the Ad26/protein preF RSV vaccine was demonstrated, in terms of geometric mean titers (GMTs) to RSV preF protein using enzyme-linked immunosorbent assay (ELISA) at 14 days post-vaccination (Day 15).

\*Note: in this protocol, “Phase 3 CTM” refers to Phase 3 CTM representative of future commercial manufacturing process material, and “Phase 2b CTM” refers to CTM representative of the Phase 2b (VAC18193RSV2001) CTM.

## OBJECTIVES AND ENDPOINTS

Objectives	Endpoints
Primary	

 
• To demonstrate non-inferiority in terms of humoral immune responses induced by vaccination with one dose of the Phase 3 CTM compared with one dose of the Phase 2b CTM
 
	
 
• pre-F ELISA antibody titers at 14 days after vaccination.
 

Secondary	

 
• To assess the safety and reactogenicity of one dose of the Phase 3 CTM compared with one dose of the Phase 2b CTM
 
	
 
• Solicited local (injection site) and systemic adverse events (AEs) for 7 days after vaccination
 
• Unsolicited AEs for 28 days after vaccination
 
• Serious adverse events (SAEs) and adverse events of special interest (AESIs) until 6 months after vaccination
 

 
• To assess neutralizing antibody responses following vaccination
 
	
 
• RSV virus neutralization antibody (VNA A2) titers at 14 days post-vaccination
 

## Hypotheses

### **Null Hypothesis:**

The Phase 3 CTM induces inferior GMTs of the pre-F ELISA titers on Day 15, compared with the Phase 2b CTM.

### **Alternative Hypothesis:**

The Phase 3 CTM induces non-inferior GMTs of the pre-F ELISA titers on Day 15, compared with the Phase 2b CTM.

Non-inferiority will be shown if the lower limit of the 2-sided 95% CI around the estimated GMR (Phase 3 CTM versus Phase 2b CTM) lies entirely above 0.67.

## **OVERALL DESIGN**

This is a randomized, double-blind, multicenter, interventional Phase 3 study in adult participants aged  $\geq 60$  to  $\leq 75$  years. A target of 240 participants will be randomized in parallel in a 1:1 ratio to 1 of 2 groups. Study vaccine will be given by the IM route.

**Table 1: Study Design**

Group	N	
1	120	Phase 3 CTM a
2	120	Phase 2b CTM b

CTM = clinical trial material; N = number of participants

a representative of future commercial manufacturing process material (Ad26.RSV.preF Lot 2 + RSV preF protein Lot b)

b representative of Phase 2b (VAC18193RSV2001) CTM (Ad26.RSV.preF Lot 4 + RSV preF protein Lot d)

After vaccination, participants will remain under observation at the study site for at least 15 minutes for presence of any acute reactions and solicited events. Any unsolicited AEs, solicited local (injection site) or systemic AEs, and vital signs (systolic and diastolic blood pressure [sitting], heart rate, respiratory rate, and body temperature) will be documented by study-site personnel following this observation period. In addition, participants will record solicited signs and symptoms in a participant diary beginning on the evening of the day of vaccination and on a daily basis for 7 days post-vaccination.

Blood will be collected from all participants to assess humoral immune responses pre-vaccination and at 14 days post-vaccination.

Safety issues that might arise from this study may be escalated to an independent Data Monitoring Committee, as needed.

The end of the study is defined as the last participant's last visit.

## **NUMBER OF PARTICIPANTS**

A target of 240 participants will be randomized in parallel in a 1:1 ratio to 1 of 2 groups.

## **VACCINATION GROUPS AND DURATION**

The study duration will be approximately 6 months per participant. The study comprises screening and vaccination for each participant on Day 1, a 28-day safety follow-up period after vaccination, and collection of SAEs and AESIs until 6 months after vaccination.

## **Study Vaccine Administration**

The active study vaccine to be used in this study is composed of Ad26.RSV.preF and RSV preF protein, to be administered as a single injection (1.0 mL) in the deltoid muscle:

- Ad26.RSV.preF (JNJ-64400141) will be used at a dose level of  $1 \times 10^{11}$  viral particles.
- RSV preF protein (JNJ-64213175) will be used at a dose level of 150  $\mu$ g.

## IMMUNOGENICITY EVALUATIONS

Venous blood samples of approximately 10 mL will be collected for the determination of humoral immune responses.

Humoral immunogenicity evaluations are summarized in the table below.

Assay	Purpose
Primary endpoint	
RSV-A pre-F ELISA*	Analysis of antibodies binding to RSV-A F protein in pre-fusion form
Secondary endpoint	
RSV A neutralization assay (VNA A2)	Analysis of neutralizing antibodies against the RSV A2 strain

ELISA = enzyme linked immunosorbent assay; VNA = virus neutralization assay

\* The same assay was used for immunogenicity assessments in the VAC18193RSV2001 (Cypress) study and will be used in the VAC18193RSV3001 (Evergreen) study

## SAFETY EVALUATIONS

Safety assessments will include the monitoring of AEs and vital signs.

AEs and special reporting situations, whether serious or non-serious, that are related to study procedures or that are related to non-investigational sponsor products will be reported from the time a signed and dated informed consent form (ICF) is obtained until the end of the study/early withdrawal. Solicited AEs, collected through a participant diary, will be recorded from the time of vaccination until 7 days post-vaccination. All other unsolicited AEs and special reporting situations, whether serious or non-serious, will be reported from the time of vaccination until 28 days post-vaccination. All SAEs, AESIs, and AEs leading to discontinuation from the study (regardless of the causal relationship) are to be reported from the moment of vaccination until completion of the participant's last study-related procedure, which may include contact for safety follow-up. All AEs will be followed until resolution or until clinically stable.

## STATISTICAL METHODS

### Sample Size Determination

Sample size calculations were performed under the following assumptions:

- no difference in the Day 15 pre-F ELISA between the Phase 3 CTM and the Phase 2b CTM (ie, assuming a true GMR of Day 15 pre-F ELISA titers equal to 1)
- a standard deviation of 1.3 at the  $\log_2$  scale for pre-F ELISA on Day 15a
- non-inferiority margin of 0.67 (2/3)
- 2-sided  $\alpha$  of 5%

A total of 105 evaluable participants per group are needed to have 90% power to demonstrate non-inferiority.

a Based on Day 15 pre-F ELISA results obtained from Cohort 2, Group 14 in study VAC18193RSV1004.

To account for exclusions from the Per-protocol Immunogenicity (PPI) Set (see below for definitions of analysis sets), drop-outs, and missing samples, approximately 120 participants per group should be enrolled.

### **Populations for Analysis Sets**

The Full Analysis (FA) Set will include all participants who received study vaccine, regardless of the occurrence of protocol deviations. All safety and participant information analyses will be based on the FA Set.

The PPI Set will include all randomized participants who received study vaccine and for whom immunogenicity data are available. Samples taken after a participant experiences a major protocol deviation expected to impact the immunogenicity outcomes will be excluded from the PPI analysis.

The list of major protocol deviations that would lead to elimination from the immunogenicity analysis will be specified in the Statistical Analysis Plan (SAP) or major protocol violation criteria document, which will be finalized before database lock and unblinding.

The primary analysis set for analyses related to RSV immunogenicity is the PPI Set. As a sensitivity analysis, key tables may also be based on the FA Set.

### **Immunogenicity Analyses**

The primary immunogenicity objective will be assessed by calculating the 2-sided 95% CIs for the difference in log-transformed Day 15 pre-F ELISA titers (ie, Group 1 versus Group 2).

The CI will be calculated via an analysis of variance (ANOVA) including both groups with Day 15 pre-F ELISA titers as dependent variable and group as independent variable. The CIs around the difference will be back-transformed (by exponentiation) to CIs around a GMR ( $GMT_{Phase\ 3\ CTM}/GMT_{Phase\ 2b\ CTM}$ ) and compared to the non-inferiority limit of 0.67 (2/3).

Non-inferiority between the Phase 3 CTM versus the Phase 2b CTM is demonstrated if the lower limit of the 2-sided 95% CI of the estimated GMR lies entirely above 0.67.

As a sensitivity analysis to assess the impact of baseline titers, the primary endpoint will also be evaluated adjusting for the respective baseline titers. For immunogenicity, baseline is considered as the last assessment pre-vaccination. In a second sensitivity analysis, different variances between the groups will be allowed. Therefore, the CIs will be calculated via Welch's ANOVA.

[figure not shown]
Finally, pre-F ELISA and VNA A2 titers will be summarized descriptively. For continuous parameters, descriptive statistics of the actual values (geometric mean and 95% CI) will be calculated at all timepoints. Additionally, geometric mean fold increases from baseline and corresponding 95% CIs will be calculated. Graphical representations of immunogenicity parameters will be created as applicable. For categorical variables, frequency tables will be presented.

### **Safety Analyses**

No formal statistical testing of safety data is planned. All safety data will be analyzed descriptively by group. All safety analyses will be based on the FA Set.

## 1.2. Schema

Figure 1: Schematic Overview of the Study

\* Screening and vaccination may be split into 2 visits in consultation with the sponsor or its delegate.

\*\* by telephone

### 1.3. Schedule of Activities

Clinic Visit #	1	2 a	3	4 a	5 a	Exit a,b
Visit Timing	Vac	Vac + 7 d	Vac + 14 d	Vac + 28 d	Vac + 6 mo	
Visit Day	1	8	15	29	183	
Visit Window		±2 d	±3 d	±5 d	±14 d	
Visit Type		Screening and VACCINATION n	Safety	Immunogenicity and Safety	Safety	Early exit
Written informed consent c	①					
Inclusion/exclusion criteria	①					
Demographics	①					
Medical history d /prestudy therapies e	①					
Vital signs f including body temperature	②					
Height and weight	●					
Randomization	①					
Pre-vaccination symptoms g	①					
Humoral immunogenicity, mL	① o 10		● o 10			
Vaccination	●					
15-minute post-vaccination observation h	●					
Solicited AE recording p	-----③-----					④
Unsolicited AE recording q	-----continuous-----					⑤
SAE recording	-----continuous-----					●
AESI recording i	-----continuous-----					●
Concomitant therapies j	-----continuous-----					●
History of SARS-CoV-2 vaccination k	-----continuous-----					●
Participant diary distribution l,m	●					
Participant diary collection and review by site staff m			●			
Approximate daily blood draw, mL	10	—	10	—	—	—
Approximate cumulative blood draw, mL	10	10	20	20	20	—

AE = adverse event; AESI = adverse event of special interest; d = days; ICF = informed consent form; mo = months; SAE = serious adverse event; vac = vaccination

① pre-vaccination; ② pre- and post-vaccination; ③ solicited local (injection site) and systemic AEs will be collected via participant diaries from vaccination until 7 days post-vaccination; ④ if within 7 days of vaccination; ⑤ if the early exit visit is within 28 days after vaccination

**Note:** At any clinic visit, an abbreviated, symptom directed physical examination may be performed if deemed necessary by the investigator based on any clinically relevant issues, clinically relevant symptoms, and medical history.

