- h. After vaccination, participants will remain under observation at the study site for at least 15 minutes for presence of any acute reactions and solicited events. Any unsolicited AEs, solicited local (injection site) or systemic AEs, and vital signs (systolic and diastolic blood pressure [sitting], heart rate, respiratory rate, and body temperature) will be documented by study-site personnel following this observation period.
- i. AESIs, including potential AESIs, are to be reported from the moment of vaccination until 6 months after the vaccination. See Section [8.3.6](#).
- j. Concomitant therapies will be collected from the time of study vaccination through 28 days post-vaccination when associated with an AE, and from ICF signature until 6 months post-vaccination when associated with an SAE or AESI.
- k. Any history of SARS-CoV-2 vaccination (name/manufacturer of the vaccine and date of administration, whenever possible) prior to and during the study will be collected in the eCRF.
- l. Rulers and thermometers will be distributed at Visit 1.
- m. Participants will be contacted by telephone 2 to 4 days post-vaccination to remind them to fill in the participant diaries and to check that they are entering information correctly.
- n. Screening and vaccination may be split into 2 visits in consultation with the sponsor or its delegate. Every effort should be made for split visits to occur preferably within 3 to 5 days and no later than 10 days, and pre-vaccination vital signs should be repeated on the day of vaccination if this visit is split.
- o. Aliquots of serum samples collected for immunogenicity tests can be reconverted for participant's safety purposes upon sponsor request. Please refer to [Table 4](#) for a non-exhaustive list of tests that may be requested to be performed on these samples in case of potential AESI reporting.
- p. Includes the assessment of the severity of solicited AEs during the Visit 2 phone call.
- q. Includes the assessment of the severity of unsolicited AEs and the occurrence of special reporting situations during all visits up to 28 days post-vaccination, including the Visit 2 and Visit 4 phone calls.

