### Visit Windows

For the following visits, windows will be allowed as indicated:

Clinic Visit #	Visit Day	Visit Window	Primary Purpose
2	8	± 2 days	7 days after study vaccination, Safety visit, by telephone
3	15	± 3 days	14 days after study vaccination, Immunogenicity and Safety visit
4	29	± 5 days	28 days after study vaccination, Safety visit, by telephone
5	183	± 14 days	6 months after study vaccination, Safety visit, by telephone

The timings of the post-vaccination visits will be determined relative to the actual day of vaccination.

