### **8.3.1. Time Period and Frequency for Collecting AE, SAE, and AESI Information**

#### **All AEs**

AEs and special reporting situations, whether serious or non-serious, that are related to study procedures or that are related to non-investigational sponsor products will be reported from the time a signed and dated ICF is obtained until the end of the study/early withdrawal.

Clinically relevant medical events not meeting the above criteria and occurring between signing of ICF and moment of vaccination will be collected on the Medical History eCRF page as pre-existing conditions.

Solicited AEs, collected through a participant diary, will be recorded from the time of vaccination until 7 days post-vaccination.

All other unsolicited AEs and special reporting situations, whether serious or non-serious, will be reported from the time of vaccination until 28 days post-vaccination.

All SAEs and AEs leading to discontinuation from the study (regardless of the causal relationship) are to be reported from the moment of vaccination until completion of the participant's last study-related procedure, which may include contact for safety follow-up. The sponsor will evaluate any safety information that is spontaneously reported by an investigator beyond the time frame specified in the protocol.

See Section [7.2](#) for procedures associated with withdrawal of consent.

All AEs will be followed until resolution or until clinically stable.

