#### **5.5.1.4. Missing Data**

Missing data will not be imputed. Participants who do not report an event will be considered as participants without an event. An AE with a missing severity or relationship will be considered as an AE reported, but will be considered as not reported for the severity or relationship. For example, an AE with missing severity will be considered as an AE reported for the analysis of any grade but will be considered as not reported for the analysis of at least grade 3. The analysis of solicited AEs will include the safety data as documented by the investigator.

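### Note 5 of the Schedule of Activities ties unsolicited-AE recording at early exit to the date of the call rather than the onset of the AE, which conflicts with Section 8.3.1 and leaves a small gap for late exits without Visit 4

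*Protocol*

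**What the plan says.** The Protocol's Schedule of Activities (Section 1.3) has an Exit column for participants who leave before Day 183. The exit contact is by telephone (footnote a). In that column, SAEs, AESIs, concomitant therapies and SARS-CoV-2 vaccination history are recorded without condition. Unsolicited AEs carry note 5 of the table key: they are recorded "if the early exit visit is within 28 days after vaccination". Footnote q places the unsolicited-AE assessment "during all visits up to 28 days post-vaccination, including the Visit 2 and Visit 4 phone calls".

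Section 8.3.1 sets the reporting period by the event, with no condition on the contact: "All other unsolicited AEs and special reporting situations, whether serious or non-serious, will be reported from the time of vaccination until 28 days post-vaccination". It also states: "All SAEs and AEs leading to discontinuation from the study (regardless of the causal relationship) are to be reported from the moment of vaccination", running to the last study-related procedure. The Synopsis says the same under Safety Evaluations.

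The Visit Windows table in Section 8 describes Visit 4 as "28 days after study vaccination, Safety visit, by telephone", on Day 29 with a window of 5 days either side.

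On the analysis side, SAP 5.5.1.4 states: "Participants who do not report an event will be considered as participants without an event". Under SAP 5.5, the denominator for unsolicited AEs is everyone in the population and phase; having been asked is not required.

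**The concern.** Note 5 tests the date of the exit call, whereas the secondary endpoint and Section 8.3.1 concern AEs that begin within 28 days. The two tests agree for an exit call made by Day 29. They diverge for a later call to someone whose Visit 4 was never completed: the AE may have started inside the period, but the schedule does not have the site record it.

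At stake is completeness of the 28-day unsolicited-AE summary, a secondary safety endpoint. The tables would not reveal the gap, because an interval nobody asked about looks the same as one in which nothing happened.

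**Working it through.** The plan gives no figure for this point, and its only design calculation (105 evaluable participants per group, Section 9.2) concerns the primary endpoint and is not involved. The check is a comparison of passages, a day count and an illustrative range.

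**1. The same call under two labels.** Vaccination is Day 1, so 28 days after vaccination is Day 29. Visit 4 runs from Day 29 − 5 = Day 24 to Day 29 + 5 = Day 34. Take a telephone contact on Day 32:

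| Labelled as | Unsolicited AEs with onset up to Day 29 | Source |
|---|---|---|
| Visit 4 | Recorded | Footnote q names Visit 4; Day 32 is in window |
| Early exit | Not scheduled | Note 5: the call is more than 28 days after vaccination |

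Nothing in the Protocol says that an exit call completes an outstanding Visit 4. After Day 34 the Visit 4 window has closed as well. Visit 5 does not help these participants, because they leave before it and have the exit call.

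**2. Length of the unasked interval.** If Visit 3 was attended, it is the last scheduled inquiry. Its window is Day 15 ± 3, that is, Day 12 to Day 18. Unasked days = 29 − day of Visit 3:

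- Visit 3 on Day 12: 29 − 12 = 17 days; 17/28 = 61%
- Visit 3 on Day 15: 29 − 15 = 14 days; 14/28 = 50%
- Visit 3 on Day 18: 29 − 18 = 11 days; 11/28 = 39%

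**3. How the SAP treats the interval.** In SAP Table 3, early discontinuation shortens the Post-dose period only if last contact precedes its planned end. With an exit call on Day 32, the whole 28 days count as observed. SAP 5.5.1.4 reads silence as no event, and SAP 5.5 keeps the participant in the denominator.

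**4. Size, under assumptions.** The documents give neither the number of such exits nor an AE rate. Let k be the number affected in a group of 120, and p the fraction of them whose first unsolicited AE fell in the unasked interval. The group percentage is then too low by 100 × k × p / 120 points.

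- k = 1, p = 5%: 100 × 1 × 0.05 / 120 = 0.04 points
- k = 3, p = 10%: 100 × 3 × 0.10 / 120 = 0.25 points
- k = 6, p = 20%: 100 × 6 × 0.20 / 120 = 1.0 point

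As an extreme, suppose the whole allowance of 120 − 105 = 15 per group were affected. The range is then 0.6 points (p = 5%) to 2.5 points (p = 20%). That allowance covers exclusions, drop-outs and missing samples for the immunogenicity analysis, so it is not an estimate of late exits.

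**The case against.** The strongest answer is that Section 8.3.1 governs and note 5 forbids nothing. Section 8.3 has AEs reported throughout the study, Section 10.2.5 requires all AEs to be recorded, and Section 8.3.2 prefers open-ended questions, which would hardly elicit only serious events. Section 7.3 requires attempts to reschedule a missed visit. Up to Day 34 a site could complete the Visit 4 items on the same call. The affected participant must also leave after Day 29, have no Visit 4 contact in an 11-day window, and still take an exit call.

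Much of this stands. The pathway is narrow, and a careful site would probably capture the events. But that relies on the site going beyond what the schedule lists for the call, and it leaves the note and the section saying different things.

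Three stronger readings are tempting, and the documents do not support them:

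- *That such a participant is never asked about AEs, or counts as event-free.* SAEs and AESIs are recorded at every exit call, and AEs recorded up to Visit 3 still count. Only the unasked interval is treated as empty, and only for other unsolicited AEs.
- *That note 5 loses AEs leading to discontinuation.* The Synopsis and Section 8.3.1 require these to be reported up to the last procedure. Section 7.2 lists an AE requiring discontinuation as a withdrawal reason and has that reason documented in the eCRF and source.
- *That early leavers are those who tolerated the vaccine poorly, so the comparison is biased.* The documents give no data on this. There is one dose, solicited reactions are collected by diary for 7 days, and the same rule applies to both blinded groups.

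**Conclusion.** The inconsistency is real but minor. Followed literally, note 5 leaves 11 to 17 of the 28 days unasked for a participant who attended Visit 3, had no completed Visit 4 and exited after Day 29. The gap is confined to unsolicited AEs that are not SAEs or AESIs and did not lead to discontinuation.

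The number affected is not stated and is probably small. With 1 to 6 affected per group and a 5% to 20% chance of a first AE in the gap, both assumed, the under-count is 0.04 to 1.0 percentage points. It falls in a descriptive summary with no formal testing. The primary immunogenicity analysis and the sample size are unaffected.

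**What to change.** Reword note 5 as: *unsolicited AEs with onset up to 28 days after vaccination not already collected at Visit 4, whatever the date of the early exit call*. Align footnote q with Section 8.3.1 by adding the exit call to the contacts it covers.

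It would also help if the safety summary reported, by group, how many participants had no unsolicited-AE inquiry covering the period to Day 29. Where exit calls have already been made, that count is what remains possible.

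The cost is one table note and one footnote in an amendment. The exit call already takes place, so no visit or procedure is added; the call becomes slightly longer. The change cannot reach participants who decline the exit call, which Section 7.2 allows for those withdrawing consent.
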